9 STATISTICAL CONSIDERATIONS

9.1 STATISTICAL HYPOTHESES

- Primary feasibility hypothesis: We hypothesize that the primary endpoint, retention at 6 months in the EMR-based outcome assessment arm, will be greater than 60%.

9.2 SAMPLE SIZE DETERMINATION

We are aiming to recruit 30 participants for the randomized outcome assessment feasibility study, with 15 in the EMR-outcome arm and equal allocation between EMR arm and the telephone arm. Using a

Bayesian design and a simulation study we assessed the probability of declaring acceptable adherence (80% credible interval that true adherence is at least 60%, $\Pr(X \geq 0.6) \geq 0.8$) over 10,000 simulated trials with sample size 15 in the intervention arm. We then summarized the results across all possible single trial outcomes and found if 11 to 15 subjects are retained, we are at least 83% confident that the true probability of retention is greater than 0.6. Thus, if at least 11 EMR arm participants meet the primary retention outcome, we will declare acceptable retention for using EMR based outcome assessment in future trials.

9.3 POPULATIONS FOR ANALYSES

Intention to treat analysis will be carried out.

9.4 STATISTICAL ANALYSES

9.4.1 GENERAL APPROACH

Categorical data will be presented using percentages and continuous data using means and standard deviations, unless the data is not normally distributed, in which case medians and ranges will be presented.

9.4.2 ANALYSIS OF THE PRIMARY EFFICACY ENDPOINT(S)

The number of EMR-arm participants who meet retention criteria will be calculated, and as described above in the sample size determination section, if at least 11 EMR-arm participants meet the primary retention outcome, we will declare acceptable retention for using EMR based outcome assessment in future trials.

9.4.3 ANALYSIS OF THE SECONDARY ENDPOINT(S)

To estimate change in quality of life (QOL) at 6 months during usual care, we will calculate individual level change in QOLIE-10 score from baseline to 6-months among all participants, with positive values (increased scores at 6 months) indicating improvement in quality of life. The mean change in QOL at 6 months (primary) will be compared to zero (no change) using the one-sample T-test with alpha=0.05, and 95% and 90% confidence intervals will be calculated. This will provide preliminary estimates of effect under usual care, to aid in sample size calculation for future intervention trials with usual care control group. Similar exploratory analyses will be carried out for change in QOL at 3 months and change in anxiety and depression scores from baseline to 3 and 6-months follow-up

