1 PROTOCOL SUMMARY

1.1 SYNOPSIS

Title:	Anxiety and depression in epilepsy: assessing outcomes using the electronic medical record (EMR)
Study Description:	
This is an observational, randomized study among N=30 individuals with epilepsy and high or borderline anxiety or depression symptoms receiving usual care at the Wake Forest Comprehensive Epilepsy Center. Participants are randomized to one of two outcome assessment methods [EMR-based-interventional method vs. telephone-based-standard method] for collecting quality of life, anxiety and depression outcomes at 3 and 6 months, under usual care management.
 
The primary aim of the study is to assess feasibility of EMR-based outcome assessment by measuring 6-month retention. We hypothesize that the primary endpoint, retention within the EMR-outcome assessment arm (defined completion of the 6 –month outcome assessment instruments via the EMR), will be greater than 60%.
 
This hypothesis will be tested by randomizing 30 patients with borderline or clinically significant anxiety or depression symptoms [Generalized Anxiety Disorder-7 (GAD-7) >7 or Neurological Disorders Depression Inventory-Epilepsy (NDDI-E) >13] to both outcome assessment methods during usual care and assessing 3- and 6-month quality of life, anxiety, and depression outcomes using the allocated outcome assessment method (N=15 in each arm).
 
We will also estimate 6-month change in epilepsy-specific quality of life in the entire study group (N=30) during usual care.

Objectives:	
Primary Objective: To assess whether retention in the EMR-based outcome method arm at 6 months is sufficient in pilot testing to support use of this outcome assessment method in future pragmatic trials of management interventions for anxiety and depression in epilepsy.
 
Secondary Objectives:
 
 - To quantify retention at 3-and 6- months in the study population using a standard pragmatic trial outcome measure (telephone outcome assessment), and at 3 months using the EMR based outcome assessment method - To estimate 6-month change in epilepsy-specific quality of life (QOLIE-10, primary outcome) and depression and anxiety (secondary) at 3 and 6 months during usual care, among the feasibility cohort of individuals with

epilepsy and borderline to high anxiety or depression scores at baseline (GAD-7>7 or NDDI-E>13 at time of screening).

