- Multiple reminders and communications will be utilized to enhance participation in the outcome assessments. Telephone calls will be scheduled at the time of enrollment if possible. The outcome instruments will be mailed to telephone arm participants 10 days before scheduled outcome calls, and they will be sent electronically 10 days prior to target completion date for EMR-arm participants. Two telephone reminders for telephone arm participants, and two electronic reminders for EMR-arm participants will be provided prior to scheduled outcome assessment. Up to 5 attempts to call participants in the telephone outcome assessment arm will be made on separate days, starting at the originally scheduled outcome assessment time. Up to 5 electronic reminders with survey instructions will be sent via the EMR to the EMR arm participants, starting with target date for EMR outcome completion.
- After criteria for retention outcome at 6 months is met (5 reminders after due date for outcome assessment as described above), to reduce potential missing data for the secondary outcomes of 6-month change in quality of life, anxiety and depression, the following will be done. For any EMR-arm participants without successful 6-month outcome collection, 3 attempts will be made to collect outcomes via telephone. For any telephone arm participants without successful 6-month outcome collection, 3 attempts will be made to collect outcomes via EMR.
- Subjects will receive incentive of \$15 gift card for completing the brief baseline telephone interview and \$15 for completing each of the two outcome assessments (3 and 6 months).
- Efforts will be made to recruit any eligible participant seen in the practice, including women and under-represented populations

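### The 6-month QOLIE-10 change promised for the whole cohort is complete-case by default, because 9.4.3 has no rule for participants without a month-6 score

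*Combined protocol and SAP*

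**What the plan says.** The synopsis (1.1) sets the target: "We will also estimate 6-month change in epilepsy-specific quality of life in the entire study group (N=30) during usual care". Section 9.3 consists of one sentence: "Intention to treat analysis will be carried out". Section 9.4.3 gives the method: "we will calculate individual level change in QOLIE-10 score from baseline to 6-months among all participants", with the mean change "compared to zero (no change) using the one-sample T-test with alpha=0.05, and 95% and 90% confidence intervals will be calculated". It also gives the purpose: "This will provide preliminary estimates of effect under usual care, to aid in sample size calculation for future intervention trials".

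Month-3 scores have their own analysis: "Similar exploratory analyses will be carried out for change in QOL at 3 months". Nothing links them to the 6-month estimate.

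Missing data are addressed only at collection. Once the 6-month retention outcome is fixed, section 5.4 allows three attempts by the other mode, "to reduce potential missing data for the secondary outcomes of 6-month change in quality of life, anxiety and depression". Section 7.2 adds a certified letter if necessary. Neither 5.4 nor 7.2 provides such other-mode attempts for a missed month-3 assessment. Section 7.1 keeps withdrawn participants in outcome assessment unless they withdrew consent.

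The available text contains no imputation rule, longitudinal model, missing-data assumption or sensitivity analysis for this endpoint.

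**The concern.** The target is everyone, but the chosen statistic can be computed only for those who answer at month 6. With no rule for the rest, software drops them silently, and the result describes responders at month 6 rather than the cohort.

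Participants are selected for anxiety or depression symptoms, so non-response could plausibly be related to baseline severity or to early course. If it is, the responder mean differs systematically from the cohort mean. This estimate is intended for planning later trials with a usual-care control group, so an error in it would carry into those plans. The schedule of activities already collects QOLIE-10 at screening, 3 months and 6 months. Part of the information needed to correct the estimate may therefore be in hand and unused.

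**Working it through.** **1. The plan's own figure.** Section 9.2 states "if at least 11 EMR arm participants meet the primary retention outcome, we will declare acceptable retention", with at least 83% confidence that true retention exceeds 0.6. With a uniform prior (assumed, since none is stated), 11 of 15 gives a Beta(12, 5) posterior and P(p > 0.6) = 0.833, which reproduces it. Ten of 15 gives 0.671, below the required 0.8. This figure concerns EMR-arm retention by the allocated method. The plan gives no numerical figure for the QOLIE-10 change.

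**2. Who enters the t-test.** The individual change is d = Y(month 6) − Y(baseline), which is undefined without Y(month 6). The number analysed is therefore 30 × final capture. The 95% half-width is t(0.975, n − 1)/√n, in units of the SD of change:

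| Final capture (assumed) | n | Half-width |
|---|---|---|
| 100% | 30 | 0.373 |
| 90% | 27 | 0.396 |
| 80% | 24 | 0.422 |
| 73% | 22 | 0.443 |
| 60% | 18 | 0.497 |

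The 73% row applies 11/15 to both arms before any other-mode contact, which is an assumption.

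**3. Bias in general.** Bias of the completer mean = missing fraction × (completer mean change − non-completer mean change). If non-completers do 0.5 SD worse (assumed), this is 0.10 × 0.5 = 0.05 SD at 10% missing and 0.267 × 0.5 = 0.13 SD at 27%.

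**4. Simulation.** All inputs are assumed: 30 participants; trivariate normal scores; correlations of 0.60 (baseline and month 3), 0.55 (baseline and month 6) and 0.70 (months 3 and 6); true change 0.20 baseline SD; logistic missingness at month 6. The likelihood estimate uses all three time points and has the same estimand as a mixed model. Biases are in baseline SD:

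| Month-6 missingness depends on | Missing | Completer mean | Likelihood estimate |
|---|---|---|---|
| Month-3 change, slope 1 per SD, all month-3 scores present | 27% | +0.14 | 0.007 or less |
| Same, 50% of non-responders also lack month 3 | 27% | +0.14 | about +0.04 |
| Same, 90% also lack month 3 | 27% | +0.14 | about +0.08 |
| Month-3 change, all month-3 scores present | 10% | about +0.05 | 0.007 or less |
| Baseline severity, all month-3 scores present | 27% | about −0.08 | 0.007 or less |
| Month-3 level, all month-3 scores present | 27% | +0.02 to +0.03 | 0.007 or less |

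In the first scenario the sampling SD was 0.199 for both estimators. Across scenarios at 27% missing with month-3 scores present, the likelihood variance was 1% to 11% lower.

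**5. Cross-check and scale.** These correlations give an SD of 6-month change of √(2 − 2 × 0.55) = 0.949 baseline SD and an SD of 3-month change of √(2 − 2 × 0.60) = 0.894. The two changes have covariance 0.70 − 0.60 − 0.55 + 1 = 0.55 and correlation 0.55/(0.894 × 0.949) = 0.65. A separate simulation built directly on change scores, with correlation 0.5 to 0.7, gave completer bias of 0.12 to 0.16 SD of change at 27% missing and 0.05 to 0.06 at 10%, in line with the table. For scale, 0.14/0.949 = 0.15 SD of change is about a third of the half-width at n = 22 (0.15/0.443 = 0.34). At 10% missing, 0.05/0.949 = 0.05 is about an eighth of the half-width at n = 27 (0.05/0.396 = 0.13).

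**The case against.** The strongest reply is that this is a preliminary secondary estimate in a feasibility pilot, the primary retention decision does not depend on it, and the plan has already acted. Other-mode contact was added specifically to protect this endpoint. That stands: the issue is modest, and it shrinks as more month-6 scores are recovered. It does not supply an analysis rule for scores still missing.

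The simulation can also be criticised as favouring the remedy, because near-zero bias requires month-3 scores for everyone who misses month 6. That stands too. Month 3 has no other-mode attempts, and the rows with 50% and 90% of non-responders also lacking month 3 show how much of the benefit is lost.

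Four stronger readings are tempting, and the documents do not support them:

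- A reader might infer that the plan expects 27% missing data here. The 11 of 15 is a minimum for success, in the EMR arm only, by the allocated method and within the window in 8.1. It precedes the other-mode attempts and is not a forecast of final capture.
- A reader might infer that a precision promised for 30 participants is not delivered. No SD, interval width or power for the QOLIE-10 change is stated anywhere.
- A reader might infer that month-3 data are thrown away. They are analysed, but separately, and do not inform the 6-month estimate.
- A reader might infer that 9.4.3 openly contradicts intention to treat. Section 9.3 does not define the term. Complete-case analysis follows from the method and the silence on missing scores; it is not stated.

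**Conclusion.** The point holds as a gap in the specification of a secondary analysis. The stated method cannot deliver an estimate for the whole cohort if any month-6 score is missing, and nothing says how such participants are handled.

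The size cannot be determined from the documents. Under the assumptions above, completer bias is about 0.14 baseline SD at an assumed pre-rescue 27% missing and about 0.05 SD at 10% when non-response depends on month-3 change. It is about −0.08 SD at 27% when non-response depends on baseline severity. Neither direction nor magnitude can be asserted in advance.

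A likelihood model reduces the bias in the scenarios examined, nearly to zero where month-3 scores exist and only partly where they do not. The case for it rests on bias, since precision hardly changes. The change is worth making because it is cheap. The primary retention rule is unaffected.

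**What to change.** In 9.4.3, make the main estimate a repeated-measures mixed model for QOLIE-10:

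- include every randomised participant with a baseline score;
- fit time as a factor (baseline, 3 months, 6 months) with unstructured covariance, REML and Kenward-Roger degrees of freedom;
- report month 6 minus baseline (primary) and month 3 minus baseline, each with 95% and 90% confidence intervals.

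Use the same model for GAD-7 and NDDI-E. Keep the one-sample t-test as a completer sensitivity analysis, and report the number contributing at each time point.

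The cost is a paragraph of wording and one standard model, with no new participants, contacts or assessments. The small downside is that the model assumes data are missing at random given the observed scores. That cannot be verified, but it is weaker than what the completer t-test needs in order to represent the cohort.

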3 OBJECTIVES AND ENDPOINTS

OBJECTIVES	ENDPOINTS	JUSTIFICATION FOR ENDPOINTS

Primary
 
To assess whether retention in the EMR-based outcome method arm at 6 months is sufficient in pilot testing to support use of this outcome assessment method in future pragmatic trials of management interventions for anxiety and depression in epilepsy.
	
-% retention in the EMR outcome arm, defined as the % of participants who complete the 6 month outcome instruments in the EMR
	
-obtain realistic estimate of feasibility of long-term EMR-based outcome assessment in this population

OBJECTIVES	ENDPOINTS	JUSTIFICATION FOR ENDPOINTS
Secondary		
To quantify retention at 3-and 6-months in the study population using a standard pragmatic trial outcome measure (telephone outcome assessment), and at 3 months using the EMR based outcome assessment method.	
-% retention at 6 months in the telephone outcome arm, defined as the % of participants who complete the 6 month outcome instruments via telephone
 
-% retention at 3 months in the EMR outcome arm, defined as the % of participants who complete the 6 month outcome instruments via telephone
 
-% retention at 3 months in the telephone outcome arm, defined as the % of participants who complete the 6 month outcome instruments via telephone
	
-to estimate future retention & develop retention strategy
 
-to assist in determining whether future studies should include telephone-or EMR-based outcome assessment for shorter and longer outcome assessment durations

To estimate 6-month change in epilepsy-specific quality of life (QOLIE-10, primary outcome) and depression and anxiety (secondary) at 3 and 6 months during usual care, among the feasibility cohort of individuals with epilepsy and borderline to high anxiety or depression scores at baseline.	
--6 month change in QOLIE-10 from baseline
 
--3 month change in QOLIE-10 from baseline
 
--change in anxiety (GAD-7) score from baseline to 3 and 6-month outcome assessments
 
--change in depression (NDDI-E) score from baseline to 3- and 6-month outcome assessments
	
-to generate preliminary estimates of effect for change in quality of life (and anxiety and depression) at 3- and 6-months from baseline during usual care, inputs that will be important for future trial planning with likely usual care control group

Tertiary/Exploratory		

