4 STUDY DESIGN

4.1 OVERALL DESIGN

This is a pilot pragmatic observational study of usual care quality-of life outcomes at 3- and 6-months among adults seen in a tertiary care epilepsy clinic. It is a feasibility pilot designed to specifically assess feasibility (retention) of a novel, EMR-based outcome assessment method among 30 adults with epilepsy and high or borderline anxiety and/or depression symptoms. Participants will be randomized 1:1 to either a traditional pragmatic outcome collection method (telephone interview) versus the EMR-based outcome assessment method. We will consider the EMR-based outcome assessment feasible if 60% of subjects in this arm are retained at 6 months. We will also assess retention in the telephone based outcome arm.

The 3- and 6-month outcome assessment instruments are brief and freely available measures amenable to future pragmatic trial use in outcome assessments (QOLIE-10, GAD-7, NDDI-E). Secondary objectives of the study include generating preliminary estimates of effect of usual care on quality of life outcomes (primary) as well as anxiety and depression outcomes (secondary).

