4.2 SCIENTIFIC RATIONALE FOR STUDY DESIGN

EMR-based tools to assess patient-reported outcomes are increasingly being proposed and used as a streamlined method for obtaining these patient reported measures and using them in care. In our previous pilot interventional study of neurologist treatment for anxiety and depression in epilepsy, we used IPad screening for anxiety and depression via REDCap to deliver standard care symptom screening and simultaneously screen individuals for potential research participation. This method required substantial coordinator effort to convey the screening results to clinicians for care purposes and to enter the results in the electronic medical record. Entry of patient reported measures directly into the electronic medical record has the potential to streamline clinical care while simultaneous pragmatic research is accomplished, because the instruments are entered as discrete data fields. Long-term outcome assessment via the patient portal interface of the electronic medical record may be feasible and potentially efficient for research staff.

In this study, we will screen patients for eligibility for the observational outcome study via implementation of standard care anxiety and depression screening and quality of life assessment directly into the patient entered section of the EMR, administered on arrival in the clinic. We will assess feasibility of EMR-based outcome assessment based on the primary endpoint of retention in the EMR-outcome arm as described above. We have decided to do a randomized feasibility trial comparing EMR outcome assessment to telephone outcome assessment, because the information from the telephone arm will also be valuable for future trial planning. This is because although telephone outcome assessment is often used in pragmatic trials, typical retention rates in epilepsy populations are unclear. Our study design aims to also assess retention using the telephone method in addition to the EMR method, to aid in determining future outcome assessment methods for interventional trials down the road. We will also use the quality of life and anxiety and depression outcome data at 3- and 6-months across the entire study population to generate estimates of long term effect of usual care among individuals with high or borderline anxiety and/or depression symptoms in epilepsy.

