5 STUDY POPULATION

5.1 INCLUSION CRITERIA

In order to be eligible to participate in this study, an individual must meet all of the following criteria:

1. Male or female, age 18 or older
2. Adequate cognition (able to complete NDDI-E and GAD-7 independently in clinic)
3. Diagnosis of epilepsy: EEG with documented seizure or epileptiform discharges OR non-epileptiform EEG and seizure remission with antiseizure drug OR treating epilepsy specialist's leading clinical impression is epilepsy
4. NDDI-E score >13 AND/OR GAD-7 score >7 at regular clinic visit at the Wake Forest Comprehensive Epilepsy Center

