5.4 STRATEGIES FOR RECRUITMENT AND RETENTION

- Target study sample size: 30 to be randomized; up to 40 consented. Anticipated number of participants to be screened: up to 1000
- Anticipated accrual rate: 5 per month

- Number of sites: 1
- Recruitment venue: clinic of Wake Forest Comprehensive Epilepsy Center, adult-focused epilepsy practices
- Participants will be identified using a learning health system care model which includes ALL patients completing the GAD-7, NDDI-E and QOLIE-10 instruments as a part of standard care upon check-in for a regular clinic visit. This will occur via a link from the clinic visit workspace to questionnaires in the patient portal interface (mywakehealth). Those who have borderline or high anxiety or depression (GAD-7 > 7 or NDDI-E >13) will be prompted to answer a question about interest in research.
- An inbasket message to study team will be triggered if an adult's GAD-7 and/or NDDI-E scores meet eligibility criteria and the individual indicates potential interest in research by answering yes to the following prompt.
 - We are doing a research study to see how patients in the epilepsy clinic with possible symptoms of anxiety or depression are doing 6 months after a clinic visit. The study includes one phone call over the next few days. Then in 3 and 6 months, you would answer some questions similar to those you just finished. Each time might take 5-10minutes.

May we contact you to tell you more about this study if you are eligible?

- When study staff receive the inbasket message, the medical chart will then be reviewed to assess whether a diagnosis of epilepsy is present. If epilepsy is present, the potential participant will be contacted by telephone and consent process will be initiated over the phone.
- For those eligible individuals who complete telephone consent for study participation, a brief baseline telephone interview focused on past psychiatric treatment history will be completed and the participant randomized. If necessary, mywakehealth activation will be done at the time of enrollment. Instructions for the allocated outcome assessment process will be provided.

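### The qualifying GAD-7 and NDDI-E scores are also the only baseline, so testing their change against zero can count regression to the mean as an effect of usual care

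*Combined protocol and SAP*

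**What the plan says.** Section 5.1 admits patients with "NDDI-E score >13 AND/OR GAD-7 score >7 at regular clinic visit". Section 5.4 describes the source of those scores: "ALL patients completing the GAD-7, NDDI-E and QOLIE-10 instruments as a part of standard care upon check-in for a regular clinic visit". The Synopsis treats the same measurement as baseline, describing the cohort as having "borderline to high anxiety or depression scores at baseline (GAD-7>7 or NDDI-E>13 at time of screening". The Schedule of Activities (Section 1.3) shows GAD-7 and NDDI-E at the screening visit, month 3 and month 6, with no repeat at enrollment. The enrollment call collects psychiatric treatment history.

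Section 9.4.3 tests mean 6-month QOLIE-10 change against zero at alpha 0.05 in all participants pooled, with 95% and 90% confidence intervals. It adds: "This will provide preliminary estimates of effect under usual care". It then extends the approach to the symptom scales: "Similar exploratory analyses will be carried out for change in QOL at 3 months and change in anxiety and depression scores from baseline".

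The result is described as an effect in several places:
- Section 4.1: "generating preliminary estimates of effect of usual care on quality of life outcomes (primary) as well as anxiety and depression outcomes (secondary".
- Section 4.2: the data will be used "to generate estimates of long term effect of usual care among individuals with high or borderline anxiety and/or depression symptoms".
- Section 3: "preliminary estimates of effect for change in quality of life (and anxiety and depression".

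Two other rules bear on the point. Section 5.2 excludes patients scoring 3 or 4 on NDDI-E item 4 at screening. Section 5.3 allows screen failures, including those whose symptoms were too low, to be screened again. Regression to the mean is not mentioned.

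**The concern.** A score above a cut-off is partly a lasting level and partly a temporary high. When the score that admits the patient is also the baseline, the temporary part tends to be gone at follow-up and the group mean falls without any true change. The cohort has no comparator that would reveal this. Both randomized arms receive usual care and differ only in how outcomes are collected, and the change analysis pools them.

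For GAD-7, the change expected when usual care does nothing is therefore below zero. A significant fall would be reported, in the plan's own terms, as an effect of usual care on anxiety when part or all of it could come from selection. Section 2.2 questions whether current medication relieves these symptoms, so that misreading would matter.

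The scales are not equally exposed. For NDDI-E, the item-4 exclusion removes some of the highest scorers at the same check-in and so offsets the fall; rescreening pushes back toward a fall. QOLIE-10 qualifies nobody and can be affected only through its correlation with the other two scales, possibly not at all.

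**Working it through.** **The plan's own figures.** The plan gives no expected change, SD of change or power for GAD-7 or NDDI-E. Its one computed design figure concerns retention: with a uniform prior, Pr(retention > 0.6 | 11 of 15) = 0.833, matching the stated 83% (10 of 15 gives 0.671). That figure is sound and is not touched by this point.

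**Inputs from the documents.**
- Entry rule: GAD-7 > 7 or NDDI-E > 13 (5.1).
- SD of 5 for GAD-7 and 4 for NDDI-E, inferred from the worsening thresholds that Section 8.5 equates with one SD.
- N = 30 (9.2).
- Test against zero at alpha 0.05 (9.4.3), taken as two-sided.

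**Assumed, not in the documents.**
- Clinic means of 5–7 (GAD-7) and 11–12 (NDDI-E).
- Six-month test-retest correlation r of 0.6–0.8.
- Correlation of 0.6 between the scales, and of 0.7 between item 4 and NDDI-E.
- 15% of otherwise eligible patients removed by item 4.
- 24 completers.

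**Step 1: one threshold, closed form.** With no true change, the expected fall is (1 − r) × SD × φ(k)/(1 − Φ(k)), with k = (cut − mean)/SD. For whole-number scores the cut is placed at 7.5 or 13.5.
- GAD-7, mean 5, r = 0.7: k = (7.5 − 5)/5 = 0.5; φ/(1 − Φ) = 0.352/0.309 = 1.141; fall = 0.3 × 5 × 1.141 = 1.71 points.
- NDDI-E, mean 11, r = 0.7: k = (13.5 − 11)/4 = 0.625; ratio = 0.328/0.266 = 1.234; fall = 0.3 × 4 × 1.234 = 1.48 points.

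These overstate the fall under the actual rule, because a patient who qualifies on one scale need not be high on the other, and because item 4 trims NDDI-E.

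**Step 2: the actual rule, by simulation.** There were 800,000 patients per scenario and 24 scenarios: two GAD-7 means, two NDDI-E means, three values of r, and cross-scale correlation over time either decaying with r or persisting. Means were identical at baseline and 6 months. Example with means 5 and 11, r = 0.7, 15% excluded, decaying correlation:
- GAD-7 change −1.10, SD of change 3.73. Standardized: 1.10/3.73 = 0.295. Noncentrality: 0.295 × √24 = 1.44. The t-test on 23 df rejects about 28% of the time.
- NDDI-E change −0.72, SD 2.99: 0.241 × √24 = 1.18; about 20%.

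With persisting correlation the changes are −0.86 and −0.30.

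**Step 3: range over the 24 scenarios, n = 24, no true change.**

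| Removed by item 4 | GAD-7 change (rejection) | NDDI-E change (rejection) |
|---|---|---|
| 0% | −0.36 to −1.52 (8–38%) | −0.18 to −1.17 (6–36%) |
| 10% | −0.40 to −1.46 (9–36%) | −0.07 to −1.01 (5–28%) |
| 15% | −0.41 to −1.46 (9–37%) | −0.02 to −0.95 (5–26%) |
| 20% | −0.43 to −1.44 (10–36%) | +0.04 to −0.89 (5–23%) |

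Further runs at 15%:
- All 30 completing: rejection 10–45% for GAD-7 and 5–32% for NDDI-E.
- A quarter to a half of the clinic screened a second time: GAD-7 −0.45 to −1.59 (10–42%), NDDI-E −0.05 to −1.07 (5–31%). Later rescreening of item-4 exclusions was not modelled.
- Whole-number bounded scores: GAD-7 −0.48 to −1.54, NDDI-E −0.03 to −1.00.
- QOLIE-10: 0 to +0.20 SD, rejection 5–19%.

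A wider grid (means 5–8 and 11–14, r 0.5–0.8, n = 30) gave GAD-7 −0.33 to −1.91 (9–62%) and NDDI-E −0.15 to −1.23 (6–42%). With a strong item-4 exclusion at means 8 and 14, NDDI-E was −0.07 to +0.03. GAD-7 fell in every run.

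**Scale of the bias.** The GAD-7 bias is 0.13–0.34 SD of change. The smallest mean change detectable with 80% power at n = 24 is 0.60 SD. In the selected cohort the baseline-to-6-month correlation drops to 0.32–0.72 from the assumed 0.6–0.8.

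**The case against.** The strongest reply is that Section 9.4.3 tests no change, not no effect. In a cohort selected on score, the mean really is expected to change, so rejecting zero is a correct statement about that cohort. The rejection rates above are error rates only against a causal null. This is right, and it locates the fault: it lies in pairing that test with the word effect. Sections 4.1 and 4.2 make the pairing for anxiety and depression, and Section 3 includes both in its estimates of effect. In 9.4.3 itself, the effect sentence follows the QOLIE-10 test and precedes the sentence on anxiety and depression.

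The stated use is planning trials with a usual-care control group, and the mean change is valid for that if the control arm is recruited by the same entry rule. The analyses are labelled exploratory and the estimates preliminary. All of this stands and limits the consequence. But those labels do not tell a reader that the change expected with no effect differs from zero, and planning needs the estimate, SD and interval rather than a p-value.

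The sizes depend on assumed inputs, and the SDs come from a safety threshold rather than from this clinic. That also stands: only the GAD-7 direction is firm, and NDDI-E bias may be nil.

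Finally, a 95% interval carries the same information as the test, so dropping the test achieves little without the caveat. Agreed; the caveat does most of the work.

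**Conclusion.** The concern holds. One check-in supplies both the entry score and the only baseline, the change is tested against zero without a comparator, and the plan calls the result an effect. With no true change, a GAD-7 fall of about 0.4 to 1.5 points is expected, and the nominal 5% test would reject 9–37% of the time at n = 24. For NDDI-E the figures are 0.0 to −1.0 points and 5–26%, with the sign not fixed if item 4 removes 20%. These sizes rest on the assumed means, correlations, exclusion share and completer count listed above. The downward GAD-7 direction held in every scenario run. The consequence is confined to interpreting exploratory secondary analyses; the 11-of-15 retention rule is unaffected. The change should be made.

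**What to change.** 1. In 9.4.3, drop the test of GAD-7 and NDDI-E change against zero. Report mean change with 95% and 90% confidence intervals, labelled as change under usual care from an eligibility-selected screening score, including regression to the mean. State that an interval excluding zero is not evidence of a usual-care effect. The QOLIE-10 test may stay, with a note that it can be affected indirectly.
2. In Sections 3, 4.1, 4.2 and 9.4.3, replace the wording about an effect of or under usual care, and about estimates of effect, with change under usual care.
3. Add the baseline-to-6-month correlation to the means and SDs already planned in 9.4.1, for later sample-size work, because selection narrows the baseline spread and lowers this correlation. It could be computed from the listings in 9.4.7, but should be planned.

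The cost is wording in four sections and one descriptive statistic, with no new data. The change neither removes nor estimates the artefact; it stops it being read as an effect. The price is a weaker claim of improvement.
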